7.3 Eligibility for optional procedures

Eligibility requirements for optional procedures are listed in Section 9.5.

7.4 Participant departure from vaccination schedule or withdrawal

This section concerns an individual participant's departure from the study product administration schedule. Pause rules for the trial are described in Section 11.4.

7.4.1 Delaying vaccinations for a participant

Under certain circumstances, a participant's scheduled vaccination will be delayed. The factors to be considered in such a decision include but are not limited to the following:

- Within 45 days prior to any study injection
 - Receipt of blood products or immunoglobulin
- Within 30 days prior to any study injection
 - Receipt of live attenuated vaccines
 - Receipt of allergy treatment with antigen injections
 - Receipt of ACAM2000 vaccine for monkeypox
 - After administration of ACAM2000 vaccine, a minimum of 30 days is required before administration of study vaccination if vaccination scab no longer present,
 - If a vaccination scab still present 30 days after receiving ACAM2000, delay study vaccination until the scab is no longer present;
- Within 14 days prior to any study injection
 - Receipt of any vaccines that are not live attenuated vaccines (eg, pneumococcal); replication incompetent vaccines such as the Jynneos monkeypox vaccine are not considered to be live vaccines

• Prevaccination abnormal vital signs or clinical symptoms that may mask assessment of vaccine reaction.

Vaccinations should not be administered outside the visit window period (see Appendix W).

In order to avoid vaccination delays and missed vaccinations, participants who plan to receive licensed vaccines or allergy treatments should be counseled to schedule receipt of these substances, when possible, outside the intervals indicated above. The effects of these substances on safety and immunogenicity assessments and their interactions with study vaccines are unknown. Therefore, if circumstances allow, these substances should also be avoided in the interval between a study vaccination and completion of the 2 or 3-week postvaccination follow-up visit.

7.4.2 Participant departure from vaccination schedule

Every effort should be made to follow the vaccination schedule per the protocol. If a participant misses a vaccination and the visit window period for the vaccination has passed, that vaccination cannot be given. The participant should be asked to continue study visits. The participant should resume the vaccination schedule with the next vaccination unless there are circumstances that require further delay or permanent discontinuation of vaccination (see Sections 7.4.1 and 7.4.3).

7.4.3 Discontinuing vaccination for a participant

Under certain circumstances, an individual participant's vaccinations will be permanently discontinued. Specific events that will result in stopping a participant's vaccination schedule include:

- Co-enrollment in a study with an investigational research agent (rare exceptions allowing for the continuation of vaccinations may be granted with the unanimous consent of the HVTN 137 PSRT)
- Clinically significant condition (ie, a condition that affects the immune system or for which continued vaccinations and/or blood draws may pose additional risk), including but not limited to the following:
 - Pregnancy (regardless of outcome) Vaccinations will be stopped while a
 participant is pregnant. If the participant is no longer pregnant and can be
 vaccinated within an appropriate visit window, vaccinations may resume
 - HIV infection
 - Any grade 4 local or systemic reactogenicity symptom, lab abnormality, or AE that is subsequently considered to be related to vaccination

- Any grade 3 lab abnormality that is subsequently considered to be related to vaccination
- Other grade 3 clinical AE that is subsequently considered to be related to vaccination with the exception of fever, and subjective local and systemic symptoms. For grade 3 injection site erythema and/or induration, upon review, the PSRT may allow continuation of vaccination
- SAE that is subsequently considered to be related to vaccination
- Clinically significant type 1 hypersensitivity reaction associated with study vaccination. Consultation with the HVTN 137 PSRT is required prior to subsequent vaccinations following any type 1 hypersensitivity reaction associated with study vaccination
- Investigator determination in consultation with Protocol Team leadership (eg, for repeated nonadherence to study staff instructions)

Participants discontinuing study product for reasons other than HIV infection should be counseled on the importance of continuing with the study and strongly encouraged to participate in follow-up visits and protocol-related procedures per the protocol for the remainder of the trial, unless medically contraindicated (see HVTN 137 Study Specific Procedures (SSP)).

Participants diagnosed with HIV infection during the study should be encouraged to participate in follow-up visits as indicated in Section 9.14.

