9.11 Visit windows and missed visits

Visit windows are included in Appendix W. The procedures for documenting missed visits and out of window visits are described in the HVTN 137 SSP. If the missed visit is one that required safety assessments or local safety labs, HVTN CRS staff should attempt to bring the participant in for an interim visit as soon as possible.

Procedures performed at an interim visit are usually toxicity/safety assessments (including local safety labs) and HIV testing. Except for HIV testing, these procedures are performed only if they were required at the missed visit or if clinically indicated. HIV testing may be performed as deemed appropriate by the study staff. Blood samples for immunogenicity assays are not typically collected at interim visits. Detail will be provided in the HVTN 137 SSP.

If a missed visit required vaccination, please refer to Section 7.4.2 and Section 7.4.3 for resolution.

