9.13 Pregnancy

If a participant becomes pregnant during the course of the study, no more injections of study product will be given. During pregnancy, no more STI testing, mucosal collections or additional optional collections will be conducted. Remaining visits and study procedures should be completed unless medically contraindicated or applicable regulations require termination from the study. During follow-up in persons who are confirmed pregnant, pregnancy testing is not required, unless clinically indicated. If the participant terminates from the study prior to the pregnancy outcome, the site should make every effort to keep in touch with the participant in order to ascertain the pregnancy outcome. Pregnancies and pregnancy outcomes will be reported as described in the HVTN 137 SSP section on Pregnancy Management and Reporting. If the participant is no longer pregnant, refer to Section 7.4.3.

If the participant is no longer pregnant (as defined by two consecutive negative tests) or breast-feeding and study product administration and mucosal and additional optional collections can be performed within an appropriate visit window, these may resume with unanimous consent of the HVTN 137 PSRT.

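### Sections 7.4.3 and 9.13 set different conditions for resuming vaccination after a pregnancy ends, and the shorter list, to which sites are referred, omits three safeguards

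*Protocol*

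**What the plan says.** Section 7.4.3 lists the events that stop a participant's vaccinations. Its pregnancy bullet halts injections during pregnancy and then lets them restart: if the pregnancy is over and the participant can be "vaccinated within an appropriate visit window, vaccinations may resume". It gives no test standard, does not mention breast-feeding and requires no approval.

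Section 9.13 opens by saying that once a participant becomes pregnant "no more injections of study product will be given". Its first paragraph ends: "If the participant is no longer pregnant, refer to Section 7.4.3". Its second paragraph then states its own rule. "If the participant is no longer pregnant (as defined by two consecutive negative tests) or breast-feeding", and dosing can be done in window, "these may resume with unanimous consent of the HVTN 137 PSRT".

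Section 7.4.2, on missed vaccinations, says: "The participant should resume the vaccination schedule with the next vaccination unless there are circumstances that require further delay or permanent discontinuation of vaccination", and cites Sections 7.4.1 and 7.4.3. Section 9.3 requires a pregnancy test before every injection and directs the reader to 9.13 for pregnant participants.

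**The concern.** One dosing decision has two rules of different strictness. The PSRT could still be undecided, or only one negative test on file, and 7.4.3 would allow the injection while 9.13 would not.

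The silence in 7.4.3 is easily read as permission. The same section names the PSRT in three other places: co-enrollment exceptions, grade 3 injection-site erythema or induration, and type 1 hypersensitivity. It also sends HIV-infected participants onward: they "should be encouraged to participate in follow-up visits as indicated in Section 9.14". The pregnancy bullet has neither feature.

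What is at stake is a safeguard that the sponsor chose. Effects on the fetus and on pregnancy are listed as theoretical risks in Section 4.6, and Section 7.2 excludes pregnant or breastfeeding volunteers.

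**Working it through.** The plan gives no figure to reproduce. The check sets the two rules side by side, traces the cross-references, and asks who could be affected.

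**Conditions for resuming**

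| Condition | Section 7.4.3 | Section 9.13 |
|---|---|---|
| No longer pregnant | Yes, no test standard | Yes, shown by two consecutive negative tests |
| Not breast-feeding | Not stated | Required |
| Within visit window | Required | Required |
| Unanimous PSRT consent | Not stated | Required |

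The count is two against four. The two-test standard defines the first condition and is not a separate one. Section 7.4.3 therefore lacks three safeguards: that definition, the breast-feeding condition and PSRT consent. The breast-feeding clause is read here as requiring that the participant is not breast-feeding; the sentence is loosely built, but the exclusion criterion supports that reading.

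**Cross-references**

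- 9.13 refers to 7.4.3 for the participant who is no longer pregnant.
- 7.4.2 refers to 7.4.1 and 7.4.3.
- 9.3 refers to 9.13, for pregnant participants.
- 7.4.3 refers to 9.14 and to the Study Specific Procedures. It does not refer to 9.13.

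**Is the second test otherwise assured?** Section 9.3 requires one pregnancy test before each injection. Appendix P (Part C, and Part B without optional procedures) schedules pregnancy tests at screening and Days 0, 56, 168 and 364, so none is scheduled between Vaccinations 2 and 3. The second consecutive negative test and the PSRT contact therefore rest on 9.13 alone.

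**Can it happen?** From the Part B and Part C visit windows in Appendix W, using the lower target and upper allowable limits:

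- Vaccination 2: 56 − 7 = Day 49 to 56 + 14 = Day 70.
- Vaccination 3: 168 − 7 = Day 161 to 168 + 14 = Day 182.
- Gap: 161 − 70 = 91 days to 182 − 49 = 133 days.

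A pregnancy found at Vaccination 2 could end in time for Vaccination 3. So could one that begins and ends between the two doses, with no dose missed.

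**Who has doses due?** Section 6.1 gives 127 participants in total, 17 in Part A and 88 in Part B. Part C is 127 − 17 − 88 = 22, with 115 − 15 − 80 = 20 vaccine and 12 − 2 − 8 = 2 placebo. In Part B, Section 4.5 reports that all 88 had at least two doses and 81 had the third as of June 7th, which leaves 88 − 81 = 7. Only participants assigned female sex at birth are relevant, and Section 7.1 requires them to use contraception, be abstinent or not be of reproductive potential.

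**The case against.** The strongest reply is that the rules are nested. Section 7.4.3 is permissive, 9.13 adds conditions, and meeting 9.13 always meets 7.4.3. When a pregnancy is found at a vaccination visit, 9.3 sends the site to 9.13, and the stricter paragraph comes directly after the sentence that refers to 7.4.3. A site goes wrong only if it stops one sentence early, or returns to 7.4.3 alone months later. This stands, and it keeps the point small. It does not remove it: 9.13 itself names 7.4.3 for exactly this case, and 7.4.3 gives a complete-looking rule.

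A reader might infer that the missed-visit rule in Section 9.11 also leads sites past the stricter conditions, since it says: "If a missed visit required vaccination, please refer to Section 7.4.2 and Section 7.4.3 for resolution". That is not supported for a participant who attends, tests positive and has the dose withheld. The dose is missed, but the visit is not.

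A reader might also infer that only Part C is exposed, because every Part B participant had received dose 2. That considers only a missed second dose. A pregnancy that starts and ends between doses 2 and 3 raises the same question for any of the 7 Part B participants whose third dose was still due.

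Finally, 9.13 cites a Study Specific Procedures section on pregnancy management that is not available here. It may repeat the PSRT step, so whether sites would act on 7.4.3 alone is unknown.

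**Conclusion.** The inconsistency is real. Section 7.4.3 states two conditions where 9.13 states four, and followed literally it permits an injection that 9.13 forbids. The documents do not support a claim that sites cannot comply with both sections or that they are never sent to 9.13.

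The consequence is rare and minor. It needs a pregnancy that ends while a dose is still due and in window, in a small group required to avoid pregnancy, and one pregnancy test still precedes every injection. No endpoint, estimate, sample size or error rate is affected. The exposed group is mainly the 22 in Part C. Whether any of the 7 in Part B were still in window when Version 5.0 was issued is not stated.

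**What to change.** In the pregnancy bullet of Section 7.4.3, replace the resumption sentence with: *vaccinations may resume only under the conditions in Section 9.13 (two consecutive negative tests, not breast-feeding, within the visit window, unanimous HVTN 137 PSRT consent)*.

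As optional tidying, limit the opening statement of 9.13 that injections stop to the time while the participant is pregnant. Its own last paragraph already allows resumption.

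The cost is one wording edit, or two with the tidying, by clarification memo, a route the version history shows this protocol already uses. No visit, test or approval is added, because 9.13 already requires them.

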7.4.4 Participant termination from the study

Under certain circumstances, an individual participant may be terminated from participation in this study. Specific events that will result in early termination include:

- Participant refuses further participation,
- Participant relocates and remote follow-up or transfer to another HVTN CRS is not possible,
- HVTN CRS determines that the participant is lost to follow-up,
- Investigator decides, in consultation with Protocol Team leadership, to terminate participation (eg, if participant exhibits inappropriate behavior toward clinic staff), or
- Any condition where termination from the study is required by applicable regulations.

8 Study product preparation and administration

CRS pharmacists should consult the Pharmacy Guidelines and Instructions for DAIDS Clinical Trials Networks for standard pharmacy operations. The protocol schema is shown in Table 3-1. See the Investigator's Brochure (IB) for further information about study products.

8.1 Vaccine regimen

The schedule of vaccination is shown in Section 3 and additional information is given below.

Part A:

Vaccination at month 6 for Group 1 and Group 2 of Part A is optional.

Group 1

Treatment 1 (T1): BG505 SOSIP.664 gp140, 100 mcg, admixed with 3M-052-AF, 1 mcg, and Aluminum Hydroxide Suspension (Alum), 500 mcg, to be administered as one 0.5 mL dose intramuscularly (IM) at months 0, 2, and 6 (optional).

Or

Placebo 1 (P1): Placebo (Tris-NaCl Buffer) to be administered as one 0.5 mL dose IM at months 0, 2, and 6 (optional).

Group 2

Treatment 2 (T2): BG505 SOSIP.664 gp140, 100 mcg, admixed with 3M-052-AF, 5 mcg, and Alum, 500 mcg, to be administered as one 0.5 mL dose IM at months 0, 2, and 6 (optional).

Or

Placebo 2 (P2): Placebo (Tris-NaCl Buffer) to be administered as one 0.5 mL dose IM at months 0, 2, and 6 (optional).

Part B:

Group 3

Treatment 3 (T3): BG505 SOSIP.664 gp140, 100 mcg, admixed with CpG 1018, 300 mcg, and Alum, 500 mcg, to be administered as one 0.5 mL dose IM at months 0, 2, and 6.

Or

Placebo 3 (P3): Placebo (Tris-NaCl Buffer) to be administered as one 0.5 mL dose IM at months 0, 2, and 6.

Group 4

Treatment 4 (T4): BG505 SOSIP.664 gp140, 100 mcg, admixed with 3M-052-AF, 5 mcg (highest tolerated dose from Part A), and Alum, 500 mcg, to be administered as one 0.5 mL dose IM at months 0, 2, and 6.

Or

Placebo 4 (P4): Placebo (Tris-NaCl Buffer) to be administered as one 0.5 mL dose IM at months 0, 2, and 6.

Group 5

Treatment 5 (T5): BG505 SOSIP.664 gp140, 100 mcg, admixed with GLA-LSQ (GLA 5 mcg, and QS-21 2 mcg) to be administered as one 0.5 mL dose IM at months 0, 2, and 6.

Or

Placebo 5 (P5): Placebo (Tris-NaCl Buffer) to be administered as one 0.5 mL dose IM at months 0, 2, and 6.

Group 6

Treatment 6 (T6): BG505 SOSIP.664 gp140, 100 mcg, admixed with Alum, 500 mcg, to be administered as one 0.5 mL dose IM at months 0, 2, and 6.

Or

Placebo 6 (P6): Placebo (Tris-NaCl Buffer) to be administered as one 0.5 mL dose IM at months 0, 2, and 6.

Part C:

Group 7

Treatment 7 (T7): BG505 SOSIP.664 gp140, 100 mcg admixed with 3M-052-AF, 3 mcg and Alum, 500 mcg to be administered as one 0.5-mL dose intramuscularly (IM) at months 0, 2, and 6.

Or

Placebo 7 (P7): Placebo (Tris-NaCl Buffer) to be administered as one 0.5 mL dose IM at months 0, 2, and 6.

Group 8

Treatment 8 (T8): Trimer 4571, 100 mcg admixed with 3M-052-AF, 5 mcg and Alum, 500 mcg to be administered as one 0.4-mL dose IM at months 0, 2, and 6.

Or

Placebo 8 (P8): Placebo (Tris-NaCl Buffer) to be administered as one 0.4 mL dose IM at months 0, 2, and 6.

8.2 Study product formulation

8.2.1 BG505 SOSIP.664 gp140

BG505 SOSIP.664 gp140 will be provided in 2 mL Type 1 glass vials with a rubber stopper and flip-off Aluminum seal. Each vial contains a fill volume of 0.6 \pm 0.05 mL at a concentration of 2 mg/mL. BG505 SOSIP.664 gp140 is a clear to opalescent, colorless to slightly yellow liquid, without any visible particles. The product is stored at \leq -65° C. The study product is described in further detail in the Investigator's Brochure (IB).

8.2.2 HIV-1 Trimer 4571 (VRC-HIVRGP096-00-VP)

Trimer 4571 will be provided as 3-mL glass vials with a 1.2 mL \pm 0.1 mL fill volume at a concentration of 500 mcg/mL. Each vial contains a sterile, aqueous, buffered solution that is clear and colorless. Some small white or translucent particles may be present. Store Trimer 4571 frozen at -35°C to -15°C.

Vials should not be refrozen after thaw. Thawed vials can be stored at 2°C to 8°C for up to 48 hours or at 15°C to 27°C for up to 24 hours. Vials are intended for single use only and do not contain a preservative. A single vial may not be used for multiple dose preparations. The study product is described in further detail in the IB.

8.2.3 Tris-NaCl buffer (TBS) (Diluent for BG505 SOSIP.664 gp140 and Placebo)

Tris-NaCl buffer will be provided in 2 mL Type 1 glass vials with 13 mm rubber stoppers and 13 mm 6-Bridge, Flip-Off, Matte Top seals. Each vial contains a fill volume of 1.1 ± 0.1 mL. Tris-NaCl buffer is a clear to opalescent, colorless to slightly yellow liquid, without any visible particulates. The product is stored at 2-8° C. The study product is described in further detail in the IB.

8.2.4 3M-052-AF (Labeled as AP 60-702)

3M-052-AF will be provided in 2 mL Type 1 glass vials with a rubber stopper and flip-off Aluminum seal. Each vial contains a fill volume of 0.4 mL at a concentration of 50 mcg/mL. 3M-052-AF is a clear to slightly hazy, colorless liquid. The product is stored at 2-8° C. Do not freeze. The study product is described in further detail in the IB.

8.2.5 CpG 1018 (Labeled as CpG 1018 Drug Product)

CpG 1018 will be provided in 2 mL Type 1 glass vials. Each vial contains a fill volume of 0.7 mL at a concentration of 6 mg/mL. CpG 1018 is a colorless, clear liquid, free of visible particles. The product is stored at 2-8° C. The study product is described in further detail in the IB.

8.2.6 GLA-LSQ (Labeled as AP 10-602)

Glucopyranosyl Lipid A (GLA) is formulated in a liposomal composition with QS-21 to generate the adjuvant GLA-LSQ. GLA-LSQ will be provided in 2 mL Type I glass vials with stoppers and flip-off Aluminum seals. Each vial contains a fill volume of 0.4 mL at a concentration of 20 mcg/mL GLA and 8 mcg/mL QS-21. GLA-LSQ is a hazy, water-white, semi-transparent liquid. The product is stored at 2-8° C. Do not freeze. The study product is described in further detail in the IB.

8.2.7 Aluminum Hydroxide Suspension (Alum)

The Aluminum Hydroxide Suspension consists of Alhydrogel® 2% (Brenntag Biosector, Frederikssund, Denmark) and will be provided in 3 mL Type 1 glass vials. Each vial contains 0.7 mL fill volume at a concentration of 5 mg/mL Aluminum. Alum appears as an opaque, white gelatinous precipitate in aqueous suspension. The product is stored refrigerated at 2-8° C. Do not freeze. The study product is described in further detail in the IB.

8.3 Preparation of study products

Pharmacists must follow appropriate aseptic technique and sterile preparation procedures/guidance as outlined in USP <797> [medium risk], utilizing a pharmacy biosafety cabinet/isolator or better. Local regulations and site institutional policies and procedures for use of personal protective equipment, such as gloves, gowns, masks, and safety glasses, must be followed. Pharmacists should follow the requirements of their country, their institution, and their pharmacy regulatory authority regarding these procedures.

Any unused portion of study product will not be used for another participant. Empty vials, unused portion of entered vials, or unused prepared study product should be discarded in a biohazard container and disposed of in accordance with institutional or pharmacy policy.

PART A:

8.3.1 BG505 SOSIP.664 gp140, 100 mcg, admixed with 3M-052-AF, 1 mcg, and Alum, 500 mcg (Group 1)

For all preparation steps, use a 1 mL Luer-Lok syringe with 0.01 mL graduations and a 22-27 gauge Luer-Lok needle.

- 1. Remove one vial of 3M-052-AF, one vial of TBS and one vial of Alum from the refrigerator. Resuspend Alum by inverting the vial for 30-60 seconds.
- 2. Remove one vial of BG505 SOSIP.664 gp140 from the freezer. Thaw BG505 SOSIP.664 gp140vial by holding in gloved hand. Once thawed, maintain the vial in upright position and gently swirl or tap the vial to mix the contents. Do not invert the vial.

Preparation of Adjuvants:

- 3. Remove one vial of Water for injection (WFI) from storage.
- 4. Withdraw 0.6 mL WFI and inject it into 3M-052-AF vial. Mix by gently swirling and inverting the vial about 5 times. Do not shake vigorously.
- 5. Withdraw 0.1 mL of the mixed preparation and inject it into an empty sterile vial (mixing vial).
- 6. Withdraw 0.2 mL of Alum and inject into the mixing vial. Mix by gently swirling and inverting the vial about 5 times. Do not shake vigorously. Allow formulation to incubate at room temperature for 30 minutes.
- 7. Withdraw 0.6 mL TBS and inject into the mixing vial. Mix by gently swirling and inverting the vial about 5 times. Do not shake vigorously.

Preparation of BG505 SOSIP.664 gp140:

8. Withdraw 0.1 mL BG505 SOSIP.664 gp140 and add it to the mixing vial. Mix by gently swirling and inverting the vial about 5 times. Do not shake vigorously.

Preparation of the Admixed Vaccine:

- 9. Withdraw 0.5 mL of the mixed preparation for study participant administration. Prior to administration, gently invert the syringe to resuspend admixed product.
- 10. The admixed product is stable for 4 hours at room temperature.

8.3.2 BG505 SOSIP.664, gp140 100 mcg, admixed with 3M-052-AF, 5 mcg, and Alum, 500 mcg (Group 2)

For all preparation steps, use a 1 mL Luer-Lok syringe with 0.01 mL graduations and a 22-27 gauge Luer-Lok needle.

- 1. Remove one vial of 3M-052-AF, one vial of TBS, and one vial of Alum from the refrigerator. Resuspend Alum by inverting the vial for 30-60 seconds.
- 2. Remove one vial of BG505 SOSIP.664 gp140 from the freezer. Thaw BG505 SOSIP.664 gp140 vial by holding in gloved hand. Once thawed, maintain the vial in upright position and gently swirl or tap the vial to mix the contents. Do not invert the vial.

Preparation of Adjuvants:

- 3. Withdraw 0.2 mL of 3M-052-AF and inject it into an empty sterile vial (mixing vial).
- 4. Withdraw 0.2 mL of Alum and inject into the mixing vial. Mix by gently swirling and inverting the vial about 5 times. Do not shake vigorously. Allow formulation to incubate at room temperature for 30 minutes.
- 5. Withdraw 0.5 mL TBS and inject into the mixing vial. Mix by gently swirling and inverting the vial about 5 times. Do not shake vigorously.

Preparation of BG505 SOSIP.664 gp140:

6. Withdraw 0.1 mL BG505 SOSIP.664 gp140 and add it to the mixing vial. Mix by gently swirling and inverting the vial about 5 times. Do not shake vigorously.

Preparation of the Admixed Vaccine:

- 7. Withdraw 0.5 mL of the mixed preparation for study participant administration. Prior to administration, gently invert the syringe to resuspend admixed product.
- 8. The admixed product is stable for 4 hours at room temperature.

PART B:

8.3.3 BG505 SOSIP.664 gp140, 100 mcg, admixed with CpG 1018, 300 mcg, and Alum, 500 mcg (Group 3)

For all preparation steps, use a 1 mL Luer-Lok syringe with 0.01 mL graduations and a 22-27 gauge Luer-Lok needle.

- 1. Remove one vial of CpG 1018, one vial of TBS, and one vial of Alum from the refrigerator. Resuspend Alum by inverting the vial for 30-60 seconds.
- 2. Remove one vial of BG505 SOSIP.664 gp140 from the freezer. Thaw BG505 SOSIP.664 gp140 vial by holding in gloved hand. Once thawed, maintain the vial in upright position and gently swirl or tap the vial to mix the contents. Do not invert the vial.

Preparation of Adjuvants:

- 3. Withdraw 0.1 mL of CpG 1018 and inject it into an empty sterile vial (mixing vial).
- 4. Withdraw 0.2 mL of Alum and inject into the mixing vial. Mix by gently swirling and inverting the vial about 5 times. Do not shake vigorously. Allow formulation to incubate at room temperature for 30 minutes.
- 5. Withdraw 0.6 mL TBS and inject into the mixing vial. Mix by gently swirling and inverting the vial about 5 times. Do not shake vigorously.

Preparation of BG505 SOSIP.664 gp140:

6. Withdraw 0.1 mL BG505 SOSIP.664 gp140 and add it to the mixing vial. Mix by gently swirling and inverting the vial about 5 times. Do not shake vigorously.

Preparation of the Admixed Vaccine:

- 7. Withdraw 0.5 mL of the mixed preparation for study participant administration. Prior to administration, gently invert the syringe to resuspend admixed product.
- 8. The admixed product is stable for 4 hours at room temperature.

8.3.4 BG505 SOSIP.664 gp140, 100 mcg, admixed with 3M-052-AF, 5 mcg, and Alum, 500 mcg (Group 4)

The highest tolerated dose of 3M-052-AF, 5 mcg, will be used in preparation of study product for administration to Group 4 participants. Follow preparation instructions in Section 8.3.2.

8.3.5 BG505 SOSIP.664 gp140, 100 mcg, admixed with GLA-LSQ, (GLA 5 mcg and QS-21 2 mcg) (Group 5)

For all preparation steps, use a 1 mL Luer-Lok syringe with 0.01 mL graduations and a 22-27 gauge Luer-Lok needle.

- 1. Remove one vial of GLA-LSQ and one vial of TBS from the refrigerator.
- 2. Remove one vial of BG505 SOSIP.664 gp140 from the freezer. Thaw BG505 SOSIP.664 gp140 vial by holding in gloved hand. Once thawed, maintain the vial in upright position and gently swirl or tap the vial to mix the contents. Do not invert the vial.

Preparation of BG505 SOSIP.664 gp140:

- 3. Withdraw 0.8 mL of TBS and inject it into an empty sterile vial (mixing vial).
- 4. Withdraw 0.2 mL BG505 SOSIP.664 gp140 and add it to the mixing vial. Mix by gently swirling and inverting the vial about 5 times. Do not shake vigorously.

Preparation of the Admixed Vaccine:

- 5. Withdraw 0.4 mL of the mixed preparation and add to GLA-LSQ vial. Mix by gently swirling and inverting the vial about 5 times. Do not shake vigorously.
- 6. Withdraw 0.5 mL of the mixed preparation for study participant administration. To maintain study blind, wait 30 minutes prior to study product delivery to clinic staff. Prior to administration, gently invert the syringe to resuspend admixed product.
- 7. The admixed product is stable for 4 hours at room temperature.

